3.4 SUBJECT SCREENING AND ENROLLMENT

Data for this study will be collected prospectively, as the patients are admitted, and assessment of their injuries matches our inclusion and exclusion criteria. Radiographic imaging from medical records will be reviewed for the purposes of screening or contacting prospective subjects. The primary investigator and

Clinical Research Associate will access the records needed for screening from CS-Link, a HIPAA compliant electronic medical records system.

3.5 SUBJECT RECRUITMENT

Patients will be recruited from all full-time orthopaedic trauma faculty. The treating surgeon and/or clinical research associate will approach patients in person to recruit, enroll and consent them for the study. No advertisement will be used for this study.

4.0 STUDY DESIGN AND METHODS

This study will be a prospective, randomized control trial. Patients will be randomized to perform distal interlock screen insertion either by freehand or distal targeting for all lower extremity nails.

1. All patients undergoing femoral or tibial nailing will undergo one method of interlock placement starting on the first of the month starting with free-hand locking. The method of interlocking screw placement will then switch to jig-based screw placement at the first of the following month. The method of screw placement will alternate each week until enrollment is complete. This method of enrollment for clinical modalities that are already in common use has previously been described with the PREP-IT trials. [Slobogean et al, JAMA Netw Open 2020]
2. Due to the nature of the distal targeting jig's construction, there may be instances where its use is not possible due to interference with other surgical instrumentation, and an intraoperative decision must be made to place screws with the freehand technique. Patients randomized to the jig-based placement arm but are ultimately treated with freehand placement will be documented and reported as crossover patients (per the CONSORT framework).
3. Patients randomized to their respective groups will ultimately undergo intention-to-treat analysis.

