A randomized controlled trial comparing free-hand versus distal targeting jig-based for distal interlock screw placement

Version 6 10/25/2023

NCT05613257

[name], FAAOS

[name], FAAOS

Cedars Sinai Medical Center

TABLE OF CONTENTS

PROTOCOL SUMMARY	3
GENERAL INFORMATION	3
1.0 BACKGROUND, RATIONALE.....	3
2.0 STUDY OBJECTIVES.....	4
3.0 STUDY POPULATION	4
3.1 SELECTION OF THE STUDY POPULATION	4
3.2 INCLUSION CRITERIA.....	4
3.3 EXCLUSION CRITERIA.....	4
3.4 SUBJECT SCREENING AND ENROLLMENT	4
3.5 SUBJECT RECRUITMENT	5
4.0 STUDY DESIGN AND METHODS.....	5
5.0 DATA COLLECTION AND MANAGEMENT	5
5.1 DATA PROCUREMENT	5
5.2 TIME PERIOD OF DATA UNDER REVIEW	5
5.3 VARIABLES COLLECTED	5
5.4 SOURCE DOCUMENTS.....	6
5.5 DATA COLLECTION AND STORAGE.....	6
5.6 CONFIDENTIALITY AND SECURITY OF DATA.....	6
6.0 DATA AND SAFETY MONITORING	6
6.1 DATA AND SAFETY MONITORING PLAN.....	6
6.2 QUALITY CONTROL AND QUALITY ASSURANCE.....	6
7.0 STATISTICAL CONSIDERATIONS.....	7
7.1 STUDY OUTCOME MEASURES.....	7
7.2 SAMPLE SIZE CONSIDERATIONS.....	7
8.0 REFERENCES	7

PROTOCOL SUMMARY

Purpose and Knowledge to be Gained	
 The purpose the research is to compare a modern proximally-based distal targeting device and free-hand techniques for placement of interlocking screws in lower extremity nailing
Research Procedures	
 The primary research procedures are using jig-based distal targeter for lower extremity nailing orthopedic surgery procedures
Subject Population	
 18 years old and above Undergoing intramedullary fixation of femur or tibia shaft for acute fracture or nonunion
Duration	
 The study includes 1 visit. The total study duration is 1 year

GENERAL INFORMATION

CSMC Co-Investigators	[name], FAAOS [name], FAAOS [name], FAAOS [name], MHDS [name], Study Coordinator
Sponsor/Funder	Stryker [name]
Collaborating Institutions Involved in the Research	N/A

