3.0 STUDY POPULATION

3.1 SELECTION OF THE STUDY POPULATION

Patients for this study will be drawn from the orthopedic trauma service. The majority of patients with these injuries will be approached in the inpatient setting, as they present through the emergency department. A small subset does present through clinic. All patients will be recruited to participate in the study after their femoral or tibia fracture repair.

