6.2 QUALITY CONTROL AND QUALITY ASSURANCE

The clinical monitor will verify that appropriate data is recorded for all study subjects for whom informed consent is obtained; and that no study specific procedures or treatments are administered without informed consent.

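### The trial is called randomised, but its only assignment rule is a foreseeable calendar alternation with unclear switching dates, and the sections bearing on when patients enrol are not reconciled

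*Combined protocol and SAP*

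**What the plan says.** Section 4.0 states "Patients will be randomized to perform distal interlock screen insertion either by freehand or distal targeting". Its first numbered item then gives one technique to all femoral and tibial nailings in a calendar period, beginning with free-hand on the first of a month. It continues "The method of interlocking screw placement will then switch to jig-based screw placement at the first of the following month", and the next sentence reads "The method of screw placement will alternate each week until enrollment is complete". In support it says "This method of enrollment for clinical modalities that are already in common use has previously been described" and cites a published trial programme. The same section undertakes to report jig-to-freehand crossovers and says "Patients randomized to their respective groups will ultimately undergo intention-to-treat analysis".

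On enrolment, section 3.1 says "All patients will be recruited to participate in the study after their femoral or tibia fracture repair", although it also describes approaching most patients as they come in through the emergency department. Section 3.4 describes prospective data collection and screening at admission. Section 3.5 lets the treating surgeon, the research associate or both obtain consent, and gives no timing. Section 6.2 has the monitor verify that "no study specific procedures or treatments are administered without informed consent". The Protocol Summary states: "The primary research procedures are using jig-based distal targeter for lower extremity nailing orthopedic surgery procedures".

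**The concern.** There are three linked difficulties.

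- **Label.** A fixed alternation with a fixed first arm contains no chance element. Anyone scheduling or recruiting can read the arm off the calendar, so the protection that the word randomised implies is absent.
- **Allocated arm.** Intention-to-treat analysis and crossover reporting both need to know which technique each patient was allocated. With month and week wording side by side and no stated transition, that cannot be settled from the text for a large share of days.
- **Timing of enrolment.** If patients are enrolled after the repair, a treating surgeon who recruits already knows the technique, how long it took and whether there was a crossover. Intention-to-treat applies only to patients who were enrolled, so it cannot correct selective enrolment.

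Placement time is not the only outcome at stake. Radiation and accuracy are also primary outcomes in section 2.0, and section 7.2 gives no effect size or SD for either.

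**Working it through.** **1. Sample size (reproduced, not in dispute).** Section 7.2 gives 616 s versus 344 s (difference 272 s), SD 192 s, 90% power and 5% significance; section 7.1 gives a two-sided test. Assuming 1:1 allocation:

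n per arm = 2 × (1.96 + 1.2816)² × 192² / 272² = 10.5, so 11 per arm and 22 per comparison.

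22 / 0.75 = 29.3, so 30 per cohort. Two cohorts give 60, and 60 / 0.91 = 65.9, so 66. All three planned figures are reproduced. On this arithmetic, 30 per cohort is the number before the 25% non-participation.

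**2. Is there a random element?** Sections 3.4, 3.5, 4.0 and 7.1 are where one would look. None gives a generated sequence, a random first arm or any concealment.

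**3. How ambiguous is the calendar?** I took 365 days from the first of each month of 2023 in turn and compared strict monthly switching with two month-then-week readings:

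| Reading compared with monthly switching | Days with a different arm |
|---|---|
| Free-hand month, then weekly alternation from month 2 starting with the jig | 163 to 169 |
| Free-hand month, jig month, then weekly from month 3 starting with free-hand | 148 to 153 |

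148/365 = 41% and 169/365 = 46%. With even arrivals (assumed), 66 × 148/365 = 26.8 and 66 × 169/365 = 30.6, or about 27 to 31 of the 66 patients.

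**4. Illustration of selective enrolment.** Assumptions, none of them in the documents: the 25% non-participation occurs after surgery, only the losses in the jig arm are selective, and non-enrolment (yes/no) correlates r = 0.1 to 0.3 with the outcome.

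Shift in the jig mean = r × SD × √(0.25/0.75) = 0.577 × r × SD. The false-positive rate of a two-sided 5% t-test with no true difference follows from the noncentral t distribution:

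| r | Shift (SD) | Shift in time | Share of 272 s | 30 v 30 | 23 v 22 | 11 v 11 |
|---|---|---|---|---|---|---|
| 0.1 | 0.058 | 11 s | 4% | 5.6% | 5.4% | 5.2% |
| 0.2 | 0.115 | 22 s | 8% | 7.2% | 6.7% | 5.8% |
| 0.3 | 0.173 | 33 s | 12% | 10.1% | 8.8% | 6.7% |

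The 30 v 30 column applies only if 60 is the pooled number left after losses. If 60 is the number before losses, 60 × 0.75 = 45, or 23 v 22. Within one cohort, 30 × 0.75 is about 22, or 11 v 11.

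Extreme bound for normally distributed times, with the slowest quarter of jig cases all missing: φ(0.6745)/0.75 = 0.424 SD = 81 s. That leaves 272 − 81 = 191 s.

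**5. Secondary: shared periods.** Section 7.1 plans a plain t-test, although every patient in a period has the same technique. The simulation used an assumed within-period correlation (ICC) of 0.01 to 0.20, patients spread at random over periods, no operator effect and no restriction on surgeon experience:

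| Patients | Periods | Type I error, plain t-test |
|---|---|---|
| 60 | 12 (monthly) | 5.6% to 16.2% |
| 60 | 52 (weekly) | 5.4% to 7.8% |
| 30 | 12 (monthly) | 5.6% to 10.7% |
| 30 | 52 (weekly) | 5.1% to 6.2% |

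**The case against.** **The interval sentences can be read in sequence:** a free-hand month, then the jig, then weekly alternation to the end. That is a fair reading, and strict monthly switching has to ignore the last sentence. Any two unsynchronised 50:50 calendars will also disagree on about half of days. Both points stand, so the 41% to 46% says only that the text does not fix the arm. Patients are already enrolled (section 7.2), so an actual calendar exists and can be written down.

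**The cited precedent may justify the method.** It might explain a design that switches technique by period, but this protocol states no random order, and a citation does not supply one.

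**Consent may be in order.** A reader might infer that the protocol plainly treats patients with a study procedure before consent. The documents do not support that. Section 4.0 says the techniques are in common use and applies them to all nailings, which leaves open that technique is service-wide practice and consent covers data only. Sections 3.1 and 3.4 suggest contact at admission, so the sentence placing recruitment after repair may be a drafting slip. Consent pages are not in the public text, so silence there proves nothing. What stands is a tension between 3.1 on one side and 3.4, and 6.2 read with the Protocol Summary, on the other.

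**The selection figures are built on assumptions.** They are, and they are offered only as an illustration. Moving planned cases across a switch date is possible with a known calendar, but no section gives the share of such cases or the discretion over their dates, so nothing is claimed for it.

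**Conclusion.** The point holds on the protocol's own wording: the trial as described is quasi-randomised, its switching rule does not fix the allocated arm, and the sections on enrolment timing need reconciling. This does not depend on any modelling.

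The size of any resulting bias is not known. Under the stated assumptions, selective enrolment after surgery would shift a mean by 0.06 to 0.17 SD. The false-positive rate would be 5.6% to 10.1% with 30 v 30 remaining, 5.4% to 8.8% with 23 v 22, and 5.2% to 6.7% with 11 v 11. A reader might quote 10% as the general figure, but it needs both the largest assumed correlation and the most favourable reading of the sample size. A reader might also infer that the planned time comparison is undermined; even the extreme bound leaves 191 of 272 s. Smaller differences in radiation or accuracy would be more exposed.

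Clustering by period is secondary: it matters for monthly periods if the assumed ICC is not small, and matters little for weekly ones.

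**What to change.** 1. In section 4.0, state one switching interval, preferably weekly, and record the calendar actually used so far.
2. For the remaining periods, draw the order of techniques by computer in randomised blocks of periods of varying size, and release each allocation only when its period begins.
3. Reconcile 3.1, 3.4, 6.2 and the Protocol Summary on when consent is taken, so that enrolment does not depend on the arm or the result. If it stays after surgery, say so and on what basis.
4. Log every eligible nailing by period and allocated technique, enrolled or not, and report enrolment by arm. Recruiters still know the arm within a period, so the log reveals selective enrolment but does not prevent it.
5. Describe patients enrolled under alternation as quasi-randomised.

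Secondary, if periods are kept: replace the plain t-test in 7.1 with period means weighted by number of patients, or with a random period effect and a small-sample correction. Period cannot be a fixed factor, because it is collinear with technique.

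**Cost.** A protocol amendment, a computer-drawn list and a log; screening is already provided for in 3.4. There is some loss of power with monthly periods. Under the simulation assumptions above, at 30 per cohort and 272 s, size-weighted period means give 83.0% to 92.0% with monthly periods (plain t-test 92.9% to 95.4%) and 93.8% to 95.4% with weekly periods (plain t-test 94.7% to 95.8%). Their type I error is 4.7% to 6.1%. This is the reason to prefer weekly periods.

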5.0 DATA COLLECTION AND MANAGEMENT

5.1 DATA PROCUREMENT

Data for this study will be procured from patient x-ray images retrieved from the picture archiving and communication software (PACS). Deidentified x-ray measurements will be stored in a HIPAA compliant Cedars Box folder.

5.2 TIME PERIOD OF DATA UNDER REVIEW

Data collection will proceed prospectively from the date of study initiation and continue for approximately 1 year.

Information will be kept for a minimum of 2 years

5.3 VARIABLES COLLECTED

- The following data points/variables will be collected:
 - Patient name
 - MRN
 - Date of surgery
 - Length of surgery
 - Type of injury

- Type of procedure
- Radiation exposure

5.4 SOURCE DOCUMENTS

Source documents for this study will be radiographic images which we will take measurements from using PACS software and incorporated into a deidentified, secure database.

5.5 DATA COLLECTION AND STORAGE

- Data will be collected and stored electronically
- Stored data will be secured via REDCap
- Only the members of the research team will have access to data
- Patients will be deidentified at time of measurement

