2.0 STUDY OBJECTIVES

Outcomes:

- Primary outcomes: radiation exposure, time, accuracy of placement (right angle to rod).
 - Each distal interlock will be considered a separate outcome
 - The first fluoroscopy shot to localize the jig or obtain a perfect circle is considered start time. The surgeon will note the hour, minute, and seconds of the time based on the wall clock in the operating room.
 - The last shot to confirm complete seating of the screw will be considered end time. The surgeon will note the hour, minute, and seconds of the time based on the wall clock in the operating room.
- Secondary outcomes:
 - accuracy of placement (right angle to intramedullary nail).
 - Number of complete misses of the nail with the drill or the screw
 - comparison of learning curve between distal targeter and freehand techniques stratified by level of training
 - The level of training of the surgeon
 - Experience level of the surgeon
 - estimated number total number of intramedullary nails placed
 - time since the last intramedullary nail placement
 - estimated number of nails placed per month over the last year
 - number of times the surgeon has used the distal targeting system
 - Comparison of tibia vs femur antegrade nails

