7.0 STATISTICAL CONSIDERATIONS

7.1 STUDY OUTCOME MEASURES

- Primary Outcome analysis: 2 tailed T-test for average length of surgery (skin to skin), average time to place 2 interlocks (start time when nail is seated and surgeon states s/he is ready to proceed with distal interlocking screw placement). Average radiation used in microGrays. Femur vs tibia average time to place 2 interlocks and average radiation exposure.
 - To compare time and accuracy of placement only data from surgeons who have performed both DT and FH techniques more than 5 times will be included.
- Secondary outcomes: t-test accuracy of screw placement (perpendicular to nail)
 - Multivariate regression evaluating predictors of time to placement
 - Level of training
 - Number of cases performed
 - Number of interlocking screws placed
 - Time since last case
 - Learning curve assessment
 - Time of each interlocking screw placement will be correlated with number of interlocking screws placed
 - Time of procedure and accuracy of placement will be analyzed in increments of 5 cases to evaluate for number of cases required to reach plateau
 - Data will be stratified by level of training

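### The plan does not mask the screw-angle reader to technique: de-identification is the only safeguard at measurement, and the surgery date points to the assigned arm

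*Combined protocol and SAP*

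**What the plan says.** **Status of the outcome.** Section 2.0 gives "Primary outcomes: radiation exposure, time, accuracy of placement (right angle to rod") and then, in its secondary list, "accuracy of placement (right angle to intramedullary nail"). Section 7.1 tests angle only under the secondary heading: "Secondary outcomes: t-test accuracy of screw placement (perpendicular to nail").

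**How it is measured.** Section 5.1: "Data for this study will be procured from patient x-ray images retrieved from the picture archiving and communication software (PACS"). Section 5.4 adds that the sources are "radiographic images which we will take measurements from using PACS software". The reader is described only as 'we'. Section 5.5 limits data access to the research team.

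**Safeguard at measurement.** Section 5.5: "Patients will be deidentified at time of measurement". Section 5.6, on confidentiality, gives name and MRN as examples of the identifiers to be removed from research records. Section 5.3 lists surgery date as a collected variable.

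**Allocation.** In section 4.0, item 1, all patients in a calendar period receive one method, beginning with free-hand. The text first describes a switch at the start of the next month and then says "The method of screw placement will alternate each week until enrollment is complete". Item 2 allows jig patients to be treated free-hand and reports them as crossovers. Item 3 specifies intention-to-treat analysis.

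No section mentions a masked or independent reader, removal of exam dates from films, random reading order, or locking of readings before linkage to technique.

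**The concern.** De-identification and masking answer different questions. The first hides who the patient is; the second hides which technique was assigned. In a trial with concealed individual randomization, removing the name and MRN might come close to doing both. Here the arm is a function of the calendar, so a date can carry the allocation even when the patient is anonymous.

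Angle is a judged measurement. Someone chooses the film and draws the lines, and the protocol defines neither the view nor the measuring rule. If expectations about the jig influenced those choices, the error would run in one direction by arm. A larger sample would not remove it.

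This route for bias is avoidable. The surgeon cannot be masked and notes the start and end times personally, so masking cannot protect placement time. A stored film can be read without knowledge of technique.

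**Working it through.** **1. Does the date identify the arm?** Setting section 4.0, item 1 beside section 5.3:
- Monthly wording: surgery date gives the month, and the month gives the assigned method.
- Weekly wording: surgery date gives the week, and the week gives the assigned method.
- The two wordings conflict and must be reconciled. Under either, surgery date plus the schedule gives the assigned arm.
- Crossovers (item 2) break the link between date and technique used, but not between date and assigned arm. Assigned arm is what the intention-to-treat analysis compares.

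**2. Does anything keep date or schedule from the reader?** Sections 5.4 to 5.6 provide de-identification, restricted access and study ID numbers. None mentions exam date, operator, technique or schedule. Inference of the arm is therefore possible and not prevented. The text does not say whether dates remain visible at the time of reading.

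**3. Group sizes for an illustration.** The plan gives no figure for angle; its sample size in section 7.2 rests on placement time. Inputs: 616 s against 344 s (difference 272 s), SD 192 s, 90% power, two-sided 5%.
- n per technique = 2 × (1.960 + 1.282)² × (192/272)² = 10.5, rounded up to 11.
- Two techniques within one bone cohort: 2 × 11 = 22.
- 75% participation: 22/0.75 = 29.3, rounded up to 30 per cohort, so 60 for tibia and femur together.
- 9% not meeting the sub-study criteria: 60/0.91 = 65.9, rounded up to 66.

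This reproduces 30, 60 and 66 when 'cohort' means bone, as the second statement in 7.2 says. Assuming an equal split by technique, 60 patients give 30 per technique overall and 15 per technique within one bone.

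**4. Illustrative effect of a differential reading shift.** Assume no true difference between techniques, one angle per patient, and a reading shift of b SDs between arms. The two-sample t statistic is then noncentral t with df = 2n − 2 and noncentrality b × √(n/2). The false-positive rate is the probability that |t| exceeds the 5% critical value (2.002 at n = 30, 2.048 at n = 15).

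| Assumed shift (SD units) | 30 per technique | 15 per technique |
|---|---|---|
| 0.1 | 6.7% | 5.8% |
| 0.2 | 11.9% | 8.3% |
| 0.25 | 15.9% | 10.1% |
| 0.3 | 20.8% | 12.5% |
| 0.5 | 47.8% | 26.2% |

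Example at 0.5 SD and n = 30: noncentrality = 0.5 × √15 = 1.94, giving 47.8%. In degrees, with an assumed SD of 2 to 4, a shift of 0.25 to 0.5 SD corresponds to 1 degree. Neither the SD nor the shift comes from the documents.

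**The case against.** The strongest reply is that de-identification is applied at the reading step itself and may, in practice, strip the exam date. Name and MRN are only examples in section 5.6, and a date held in the database need not be visible to the person measuring. This stands in part. A reader might infer that the angle readings are unmasked, or that the arm will be read off each film. The documents do not support that; they show only that nothing rules it out. Even full removal of dates would leave the operative note, the schedule and a surgeon-reader's own memory of the case uncontrolled.

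A film's date is also not necessarily the surgery date. The protocol does not say which film is measured, and under weekly alternation a later film could fall in the other technique's week. This stands. Inference of the arm requires the surgery date and the schedule, not merely any date on a film.

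Third, it is tempting to say that a primary endpoint is compromised. The documents do not support this without qualification: angle is in both lists in section 2.0, it is tested only as secondary in 7.1, and the sample size is built on time.

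Finally, the error rates are hypothetical. Section 7.1 restricts the accuracy comparison to surgeons who have performed each technique more than 5 times, so 30 per technique is nearer a ceiling. Section 2.0 treats each interlock as a separate outcome, which the one-angle-per-patient calculation ignores. Both points stand, but the omission does not depend on the figures.

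**Conclusion.** The point holds as an unprevented risk, not as demonstrated bias. The study team reads the angle, surgery date and schedule together give the assigned arm, and the only stated safeguard protects privacy. This is a minor, inexpensive improvement to the design, and it applies whether angle is finally classed as primary or secondary.

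Its size cannot be estimated from the documents. The range of about 16-48% at 30 per technique (10-26% at 15) follows from an assumed differential shift of 0.25 to 0.5 SD and shows only how a test responds to such a shift. A reader might take it as the false-positive rate this trial faces; nothing in the documents supports that, and a shift of 0.1 SD would give under 7%. The conclusion is confined to the film-based angle and does not extend to placement time or radiation dose.

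**What to change.** In sections 5.4 and 5.5, replace the present measurement step with a masked reading procedure:
- Export the final films under study ID with exam date, operator and other case information removed.
- Have a current research-team member who did not operate on the case measure them in random order, without access to technique, operative note or schedule.
- Lock the readings before linking them to the assigned arm.

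In the same revision, reconcile the status of angle between sections 2.0 and 7.1, and the monthly and weekly wordings in section 4.0, item 1.

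The cost is a short export step per case and a restriction on which existing team member reads each film. No extra imaging or patients are needed, and the sample size is unchanged. Because the films are held in PACS, the procedure can also be applied to those already acquired.
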